Study Protocol and Statistical Analysis Plan

Title of Study: Parent Resource About Pediatric Clinical Trials

ClinicalTrial.gov Identifier: NCT07233967

Principal Investigators: [name]; [name]

Date of Document: 05/19/2025

Table of contents

	Page number
Study Protocol	3
Objectives	3
Design	3
Methods	4
Statistical Analysis Plan	7

Study Protocol

Objectives:

To develop and test the effectiveness and safety of medical and behavioral treatments for children and adolescents, pediatric clinical trials are needed. However, some clinical trials experience difficulty with recruitment of families due to a number of reasons, such as time or travel limitations, potential risks to child, mistrust, or lack of information. Providing relevant and high-quality information to parents can positively contribute to decision-making as well as recruitment and enrollment in future clinical trials. The Pediatric Clinical Trials (PCT) Pocket Guide is an interactive, online resource designed to increase parents' awareness and understanding of clinical research and their ability to communicate with others about research, and willingness to participate in a clinical trial. The objective of this project is to examine the feasibility of the PCT Pocket Guide in a randomized controlled trial with parents of children between the ages of 7 and 17 years. Parents will complete pre- and posttest assessments, which will provide information on the acceptability, appropriateness, and feasibility of the PCT Pocket Guide and a preliminary test of the Pocket Guide's efficacy for improving outcomes related to knowledge, attitudes, self-efficacy, trust, and willingness and likelihood of participating in pediatric clinical trials.

Design:

The study type is interventional and the study model is parallel assignment with a 1:1 allocation ratio and superiority framework to examine the feasibility of the PCT Pocket Guide. The randomized controlled trial will be conducted online at two time points: 1) baseline/pretest and 2) posttest (two weeks after pretest). The study questionnaires will be programmed into an online data collection system. The resources (intervention and active control) will also be completed online by participants. Participants will be randomized, stratifying based upon race/ethnicity (white and not Hispanic/Latino; nonwhite and/or Hispanic/Latino) to one of two conditions: 1) intervention (access to PCT Pocket Guide) or 2) active control (access to control materials compiled from a NIH-supported website). Participants are randomized and enrolled based on: 1) time study forms (i.e., consent) were completed, 2) confirmation of email addresses, 3) their reported demographics collected in the eligibility screener questions, 4) address verification, and 5) indication that they learned about the study from one of the targeted school districts. One of the Co-Principal Investigators will generate the allocation sequences using a random number generator in Excel, assign participants to condition (either intervention or active control) according to those sequences, and enroll participants in the study. The allocation sequence will be stored in a folder on a secure, password-protected server. All participants will be assigned a unique ID number that will be associated with their data (questionnaires; resource use) in place of their name. All personally identifiable information (PII) will be saved on iRT's password protected server, and kept separate from data.

Methods:

Sample and Recruitment.

Parents of children aged between 7 and 17 years will be recruited for the study from across the United States. To be eligible to participate in the study, the following criteria must be met: a) adult participant is a parent or legal guardian of adolescent participant child between ages 7 and 17; b) parent has access to a computer or tablet or smart phone with internet connection (as the resources and questionnaires are web-based); c) participant's child attends school where recruitment flyers have been sent or report that they heard about the study from one of the study recruitment partners; 4) parent is fluent in English or Spanish; and 5) parent has not allowed their child to participate in a clinical trial in the past. A study recruitment website will contain information about the research study and study team contact information that interested parents can review. The website will include a link to the study's eligibility screening questions. Parents will be asked to indicate their race, ethnicity, sex, and child/children's ages to assist in ensuring a diverse sample of participants. Parents will also be asked to respond to questions about previous clinical trial participation and trust related to clinical trials. Parents will also be asked which language they would prefer to use for the study (English or Spanish) and this information will be used as part of the enrollment process to enroll eligible parents in the study in their preferred language. Parents will also be asked where they heard about the study (e.g., social media, school, community or health organization) and will be asked to specify which school or organization. Study flyers will be used to recruit parents; we will identify school districts with diverse student populations and share the recruitment flyers via PeachJar, a digital flyer service within school districts. The English versions of the study materials and resources will be translated into Spanish.

Procedure.

Parents who are eligible to participate in the study will be given access to the online consent form. Parents will read the consent form and provide online consent by typing their names into a text box, providing contact information, and clicking a button to indicate consent. They will have the option to download and/or print the forms to retain a copy for their files. Interested participants who decide to complete the forms will be told that in an attempt to have a diverse sample, they may not be invited to participate. Potential parents will be provided with the contact information of the researchers and may contact them to ask any questions they may have about the study. If they contact the research team and have not yet been screened for eligibility, they may be screened using the same set of questions on the recruitment website over the phone with a project staff member. On the consent form, participants will be asked for their preferred email address to receive study communications and incentives (i.e., gift cards) over the study period. Before receiving communications at this email address, they will need to verify that they can receive emails at this address by clicking a link that is emailed to them. Parents will also be asked on the consent form to agree to receiving study communication via text. Before receiving text communications at their phone number, they will need to verify that they can receive texts at their number by clicking on the verification link that is sent via SMS message. Only parents with completed study forms will be permitted to participate in the study. iRT project staff will

determine whether or not the address the parent has provided in the consent form is real such as a Google search.

If there is space in the study, consented and verified participants will be randomly assigned to either the intervention group or active control group based on a randomly generated number table. When the study starts, parents will receive an enrollment email/text from the study management system via the parent's email address (and text message) with a link for the participating parent to complete the online parent pretest questionnaire within one week. If the parent completes the questionnaire, they will be eligible for a \$20 gift card. Upon completion of the pretest questionnaire, parents will receive a message at the end of the questionnaire informing them of their next steps in the research study.

- a. Participants in the intervention group will then be provided via email/text with a link to access the resource (PCT Pocket Guide). They will be asked to review the resource within two weeks.
- b. Participants in the active control group will be provided via email/text with a link to access the control materials [articles and videos compiled from a NIH-supported website (Children and Clinical Studies) into one online resource]. They will be asked to review the resource within two weeks.

Project staff members will monitor resource usage by groups through the LMS. Parents who complete the resources within 2 weeks will receive a \$25 gift card. Approximately two weeks after completing the pretest questionnaire, participants will receive an email and text with a link to access to their online posttest questionnaire. This questionnaire will include the same questions and instructions at pretest as well as consumer satisfaction questions. If the parent completes the questionnaire, they will receive a \$30 gift card. Participants will receive automatic email/text reminders from the study management system if they have not completed the questionnaires or not accessed their assigned online resource.

Measures.

Implementation

The Learning Management System (LMS) will record the amount of time that participants spend with the parent resource (PCT Pocket Guide; active control) and the specific components that were reviewed.

Consumer Satisfaction

Data will be collected on participant feedback about the resource they review through a posttest consumer satisfaction questionnaire (CSQ). The CSQ will consist of the Acceptability of Intervention Measure (AIM), Intervention Appropriateness Measure (IAM), and Feasibility of Intervention Measure (FIM), which are 4 items each using a 5-pt. Likert scale (1=Completely disagree to 5=Completely agree) and have good discriminant validity and reliability (Weiner et al., 2017). Higher scores indicate greater acceptability, appropriateness, and feasibility. Participants will also be asked to rate their satisfaction with the resource's content, format, and usability using a 5-point Likert scale (1 = Strongly disagree to 5 = Strongly agree) with higher

scores indicating greater satisfaction with the resource. Participants will also respond to open-ended questions about what they liked best and least and any suggestions for changes for their assigned resource.

Outcomes

Likelihood of participation in clinical trials. Parents will be asked to respond to one question about the likelihood of allowing their child to participate in a clinical trial (i.e., “If your child were asked to be in a clinical trial, how likely would you be to let them participate?”) and will respond using a 5-point Likert scale (1 = Not likely at all; 2 = Not very likely; 3 = Moderately likely; 4 = Very likely; 5 = Extremely likely). Parents will also be asked to respond to one question about the likelihood of their fear preventing them from allowing their child participate in a clinical trial (i.e., “How likely is it that your fearful or anxious feelings could stop you from allowing your child to participate in a clinical trial in the future?”). Parents will respond using a 5-point Likert scale (1 = Not likely; 2 = Somewhat likely; 3 = Moderately likely; 4 = Very likely; 5 = Extremely likely).

Willingness to participate in a clinical trial. Parents will review up to five research protocols related to a fictitious disease (‘meditis’) and respond to questions about their willingness to let their child participate in each research study (i.e., “If your child had meditis, would you agree to enroll them in this study?”; 1 = Definitely not to 7 = Definitely yes; and “If you had to say for sure, what would your answer be?”; 0 = No; 1 = Yes). Parents can also describe the reason for their decision in an open-ended space. Parents will also be asked about decision-makers in the decision to participate (i.e., “Who should make the final decision on whether or not your child will participate in this research study?”; 1 = my child; 2 = mostly my child; 3 = joint decision; 4 = mostly me; 5 = me). The final two questions will ask about the risk and benefits of participating in each study (i.e., “Overall, how risky is this study for your child?”; “Overall, how beneficial is this study for your child?”; 1 = Not at all to 7 = Extremely). This measure is adapted from Brody et al. (2005).

Knowledge. This measure will be created for the purposes of this study based on the content in the parent resource. Parents will respond to fact-based questions in multiple choice format that assess their knowledge about clinical research (e.g., “What does giving assent mean?”; “Once your child agrees to be in a clinical trial, can they stop before the trial is over?”).

Familiarity with clinical trials. Parents will be asked to respond to one question about their familiarity with clinical trials [“How much do you know about pediatric clinical trials (research studies with children under 18)?”; 1 = I don’t know anything; 2 = I know a little about them; 3 = I know some things about them; 4 = I know a lot about them; 5 = I know all there is to know about them.]

Attitudes and beliefs. Six items will assess their positive attitudes about clinical trials (e.g., How do you feel about kids participating in clinical trials?; 1=Not good at all; 2=Not very good; 3=Not sure; 4=Good; 5=Very good; $\alpha=.91$; adapted from Madsen, Mirza, Holm, Hilsted, & Riis, 2002) and five items will assess their beliefs about positive aspects of pediatric clinical research (e.g., I believe that clinical trials can help kids; 1=Strongly Disagree; 5=Strongly Agree).

Decision Self-Efficacy. To assess self-efficacy for making decisions, parents will be asked to respond to 11 questions including confidence in obtaining information, asking questions, and making an informed decision (“Get the facts about the risk and side effects of each choice.”). These items will be adapted to reflect a decision about their child’s participation in a clinical trial. Parents will respond to each question using a 5-point Likert scale (0 = Not at all confident; 4 = Very confident; adapted from O’Connor, 1995).

Research trust/mistrust. Parents will be asked to respond to 10 items using a 5-point Likert scale (1 = Strongly Disagree; 5 = Strongly Agree) to assess research trust/mistrust. The measure has four factors, including General Trustworthiness; Perception of Deception; Perception of Exploitation; and Perception of Discriminatory Treatment (Smirnoff et al., 2018).

Statistical Analysis Plan

Data will be analyzed using SAS 9.4.

Preliminary analyses. Psychometric analyses will be conducted to examine the reliability, validity, and distributions of key variables and scales. Handling variables with poor reliability or validity will include modification or elimination of such variables from the analysis data sets. Variables with noticeably skewed distributions will be transformed or categorized to reduce the impact of non-normality on subsequent analyses. Descriptive statistics will also be conducted to examine the distributions, correlations, means, and standard deviations of the outcome variables. Preliminary analysis will include a test of equivalency between the intervention and control groups on demographic characteristics and baseline levels of primary outcome variables using chi-squared analyses for categorical variables and t-tests for continuous variables. Any characteristics that are nonequivalent will be added as covariates in the main analyses. Depending on the level of missingness, missing data will be multiply imputed at the item level. The imputation model will be estimated using the PROC MI procedure in SAS and will include all outcome items and demographic characteristics that will aid in estimating missing data values. Main analyses will be conducted on each of the imputed datasets.

Main Analyses. Parents’ reports on the acceptability (AIM), appropriateness (IAM), and feasibility (FIM) of both the intervention (PCT Pocket Guide) and active control (NIH-supported website materials) will first be examined through descriptive statistics. Group mean scale scores greater than 3.0 will indicate more than a moderate amount of acceptability, appropriateness, and feasibility for each resource. Next, ANCOVAs will be used to compare AIM, FIM, and IAM scores looking at main effects of condition as well as interactions (parent gender, parent race/ethnicity, child age, research mistrust), including relevant covariates from the preliminary analyses. We will examine the resource completion rates (at least 70% complete) in the entire intervention group, as well as in subpopulations (parent gender, parent race/ethnicity, research mistrust, research familiarity), as another measure of feasibility. Finally, open-ended feedback about what was liked most, least, and suggested revisions will be coded into categories and summarized. The feedback will be used to create a list of necessary edits to increase the relevance of the resource for parents overall, and for subpopulations of parents.

Exploratory Analyses. To examine intervention effects on the outcome variables at posttest, multiple regression analyses will be used with condition (intervention; active control) as the independent variable. Pretest scores for each outcome will be included as predictor variables and outcome variable means will be reported as adjusted posttest scores. Analyses will be intent-to-treat. Demographic characteristics found to be non-equivalent between the two groups will be included as covariates in the regression models. In addition, moderator analyses will examine intervention effects for subpopulations (e.g., race/ethnicity, sex, research mistrust) to provide evidence regarding how the impact of the PCT Pocket Guide may potentially vary as a function of these characteristics.

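### One Co-Principal Investigator generates the allocation list, assigns condition and enrols participants, so allocation is not concealed from the enroller, and no strict order of entry limits the resulting discretion.

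*Combined protocol and SAP*

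**What the plan says.** **Roles (Study Protocol, Design).** One sentence covers all three tasks: "One of the Co-Principal Investigators will generate the allocation sequences using a random number generator in Excel, assign participants to condition", then "according to those sequences, and enroll participants in the study". The subject of all three verbs is the same investigator.

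**Protection of the list (Design).** "The allocation sequence will be stored in a folder on a secure, password-protected server". The protocol does not say who can open the folder. It describes no independent list holder, automated release or other concealment step.

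**Basis for entry (Design).** "Participants are randomized and enrolled based on: 1) time study forms (i.e., consent) were completed". Four further items follow: email confirmation, "their reported demographics collected in the eligibility screener questions", address verification, and having learned of the study through a targeted school district. No ranking, quota or tie rule is attached to the five items.

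**Limits on entry (Methods, Procedure).** Parents who complete the forms are "told that in an attempt to have a diverse sample, they may not be invited to participate". Consented and verified parents are assigned only if the study still has room. This section describes assignment a second time, by a randomly generated number table, and again names no independent person or system.

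**Analysis (Statistical Analysis Plan).** Preliminary analyses test the arms for equivalence on demographics and on baseline levels of the primary outcome variables, and add any non-equivalent characteristic as a covariate. Main Analyses compare AIM, IAM and FIM between arms by ANCOVA. Exploratory Analyses regress each posttest outcome on condition and its pretest score.

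**The concern.** Randomisation protects a comparison only if the decision to admit a person is made without knowledge of the arm that person will receive. Here the person who enrols wrote the list. If that person also has any latitude over who enters next, the mix of parents can differ between arms for reasons other than chance. This need not be deliberate: a mild preference for a particular kind of parent, exercised when a particular assignment is due, is enough.

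At stake is the between-arm comparison in a trial that the Design section describes as 1:1 and superiority. The Main Analyses comparison of AIM, IAM and FIM is the most exposed, because these scales rate the resource just reviewed and so have no pretest. The preliminary efficacy results are exposed too, though less so. A tilted intervention arm could also shift the two criteria judged within an arm: a mean above 3.0 for each resource, and the 70% completion criterion in the intervention group.

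**Working it through.** The point concerns procedure. The documents give no sample size, power or effect size to reproduce, so the check is to set the provisions side by side and ask two questions.

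**1. Can the enroller know the next assignment?** Yes. The investigator creates the sequences in Excel and assigns from them. Storage on a secure server keeps outsiders away from the list but not its author. Stratifying by race/ethnicity in two strata does not change this, because the author knows the next entry in each stratum.

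**2. Does the enroller have discretion over who enters next?** The provisions point in both directions.

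| Provision | Effect on discretion |
|---|---|
| Form-completion time listed as a basis for entry (Design) | Limits it, if applied strictly; the text does not say that it is |
| Online self-screening and consent, email confirmation, address check by project staff (Procedure) | Limits it; these are largely objective checks |
| Reported demographics as a basis for entry (Design) | Leaves it open; they supply the stratum, but no quota or target is given |
| Consenting parents may not be invited, for diversity (Procedure) | Leaves it open; eligible parents can be passed over, by no stated rule |
| Assignment only if there is space (Procedure) | Leaves it open; no rule says who is left out when places are short |

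The answer is therefore: some discretion, of unspecified extent. Stratification does not close the gap. It addresses race/ethnicity only, whereas the screener also records sex and children's ages to help obtain a diverse sample. Parent gender and child age are among the interaction factors planned for the AIM, IAM and FIM models.

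**3. Would the planned analysis remove a tilt in entry?** Only in part.

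- Covariates enter when a chi-squared or t-test finds non-equivalence. Such tests can miss a modest imbalance and cannot see an unmeasured one.
- Pretest adjustment applies to the exploratory outcomes. It cannot apply to AIM, IAM and FIM.
- The pretest is sent after assignment (Procedure), so baseline data come only from parents already admitted and allocated.

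**4. Size.** If a share *s* of entries were steered, and steered parents differed between arms by *d* on an outcome, the bias in the mean difference would be *s* × *d*. The documents give neither *s* nor *d*, nor an effect size to set the product against. Any numerical value would be an assumption.

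**The case against.** The strongest reply is that the protocol says this investigator enrols, not that the investigator picks. Time of form completion is the first item listed, parents screen themselves and consent online, and project staff check addresses. Demographics have an innocent use, since they supply the stratum. If time order were followed strictly within stratum, little room to steer would remain. That is correct, and it is why the point is limited to an unstated order combined with an unconcealed list. It does not dispose of the point, because strict order is not stated and the diversity clause tells parents that they can be passed over.

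A second reply is that the aim is feasibility and the efficacy analyses are labelled exploratory. This lowers the stakes but does not remove them: the AIM, IAM and FIM comparison sits under Main Analyses.

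A reader might infer more than the documents support:

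- *That the enroller uses parents' trust in trials.* The screener asks about it, but nothing says that the enroller sees the answers.
- *That nothing corrects a tilted entry.* Detected imbalances become covariates, research mistrust is an interaction factor in the AIM, IAM and FIM models, and the exploratory outcomes are adjusted for pretest.
- *That every outcome is self-reported opinion.* Resource use is logged by the learning management system, and knowledge is tested with factual multiple-choice questions.
- *That steering takes place.* The documents show only that the procedure allows it.

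**Conclusion.** The point holds in this form: as written, allocation is not concealed from the person who enrols, and the entry rules leave that person an unspecified amount of discretion, so the design permits selection bias. The lack of concealment follows directly from the Design section. The discretion is an inference from the absence of an ordering rule together with the demographics, diversity and space provisions; a strict time order in practice would largely remove it. The direction and size of any bias cannot be estimated from the documents. The planned adjustments mitigate it in part, more for the exploratory outcomes than for AIM, IAM and FIM. Because analysis cannot restore concealment afterwards, the change belongs before allocation starts.

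**What to change.** Replace the sentence on roles in the Design section, and align the Procedure section with it:

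1. An existing team member with no role in enrolment, for example the other Principal Investigator, generates and holds the list for the two race/ethnicity strata.
2. The protocol states in advance the order of enrolment within stratum, for example by form-completion time, and any demographic targets, including how a parent comes to be passed over.
3. The enroller records a final, time-stamped decision to enrol. Only then does the list holder release the next assignment. The study management system could do this instead if it is able to; the documents describe it only as sending messages and reminders, so this should be checked first.

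The cost is revised wording and a small hand-over step between existing staff, with no additional staff or participants. If enrolment has already begun, document the order actually used and report the lack of concealment as a limitation.

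### The race/ethnicity randomisation stratum is not a fixed covariate in the main-effect models: the SAP adds it only if a baseline test finds the arms unequal

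*Combined protocol and SAP*

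**What the plan says.** **Allocation.** The Design section describes "parallel assignment with a 1:1 allocation ratio and superiority framework" and randomises participants "stratifying based upon race/ethnicity", in two strata: white parents who are not Hispanic or Latino, and all other parents. One Co-Principal Investigator is to "generate the allocation sequences using a random number generator in Excel". The Procedure section says that participants are "randomly assigned to either the intervention group or active control group based on a randomly generated number table". Neither place mentions blocks, permutation or any other restriction within strata, and neither says that the sequences are unrestricted.

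**Covariates.** Under Preliminary analyses, the SAP plans a "test of equivalency between the intervention and control groups on demographic characteristics and baseline levels of primary outcome variables", using chi-squared tests and t-tests with no significance level given. Characteristics that fail become covariates in the main analyses. Exploratory Analyses repeats the rule for efficacy: "Demographic characteristics found to be non-equivalent between the two groups will be included as covariates in the regression models". The pretest score is always in those regressions. The randomisation stratum is not named as a fixed term.

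**Other uses of race/ethnicity.** Under Main Analyses, parent race/ethnicity is one of the interactions examined in the ANCOVAs of the acceptability, appropriateness and feasibility scores (AIM, IAM, FIM). Under Exploratory Analyses it is a planned moderator. Neither use depends on the baseline test.

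**The concern.** A factor used to stratify randomisation belongs in the analysis model. Restricted randomisation within strata removes between-arm variation due to that factor. A model that omits the factor still counts that variation as residual noise, so its standard error for the condition effect is too large.

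A test-driven rule works against this. The better the stratification balances the arms, the less likely the test is to flag the stratum, and so the less likely the stratum is to enter the model. The test also addresses the wrong question. In a randomised trial a baseline difference arises by chance, and its p-value says nothing about how strongly the factor predicts outcome, which is what determines the gain from adjustment.

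At stake is some precision in the between-arm comparisons. Race/ethnicity is the only factor the design chose to stratify on.

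**Working it through.** **Inputs from the documents.** 1:1 allocation; two strata; covariates added only on a failed baseline test. The documents state no sample size, power, significance level, effect size or SD, so there is no figure of the plan's own to reproduce.

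**Assumptions.** Total N of 60 to 300 for balance, and 100 and 200 for error rates and power; stratum share q of 30% or 50% for balance, and 50% for error rates and power; tests at 5%; treatment effect 0.4 SD; stratum effect 0.3, 0.5 or 0.8 SD, in units of the within-stratum SD. Two kinds of list were compared: unrestricted within strata, and blocks of 4 within strata. There were 5,000 runs per setting, so the Monte Carlo standard error of a 5% rate is √(0.05 × 0.95 / 5,000) = 0.3 points. No pretest was modelled. For the exploratory regressions, the stratum effect should be read as what remains after pretest adjustment.

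**Step 1: how often does the baseline test flag the stratum?** Across N = 60 to 300:
- Unrestricted lists: 4.9% to 5.4% of trials, as expected of a 5% test.
- Blocks of 4: 0% of trials.

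**Step 2: restricted lists, stratum omitted.** With within-stratum variance 1 and stratum effect d, the model without the stratum estimates a residual variance of 1 + d²q(1−q). The variance that applies to the condition contrast is 1. The standard error is therefore too large by a factor of √(1 + d²q(1−q)), and the true type I error is about P(|Z| > 1.96 × that factor). At q = 0.5:

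| d | Residual variance | SE factor | Approximate type I error | Simulated, N=100 / N=200 |
|---|---|---|---|---|
| 0.3 | 1 + 0.09 × 0.25 = 1.0225 | 1.011 | 4.7% | 4.9% / 4.6% |
| 0.5 | 1 + 0.25 × 0.25 = 1.0625 | 1.031 | 4.3% | 4.2% / 5.0% |
| 0.8 | 1 + 0.64 × 0.25 = 1.16 | 1.077 | 3.5% | 3.3% / 3.6% |

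With the stratum always in the model, simulated type I error is 4.8% to 5.6%.

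**Step 3: unrestricted lists, conditional rule.** Simulated type I error is 4.3% to 5.2%, so validity is not at issue.

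**Step 4: power, conditional rule against always including the stratum.**

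| Lists | d | N=100 | N=200 |
|---|---|---|---|
| Blocked | 0.3 | 49.3% → 50.0% | 80.2% → 80.8% |
| Blocked | 0.5 | 49.2% → 51.8% | 78.9% → 80.9% |
| Blocked | 0.8 | 45.1% → 50.8% | 75.8% → 80.5% |
| Unrestricted | 0.3 | 48.5% → 49.1% | 80.0% → 80.4% |
| Unrestricted | 0.5 | 47.3% → 49.4% | 77.2% → 79.2% |
| Unrestricted | 0.8 | 45.8% → 49.9% | 74.9% → 80.7% |

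The loss is under 1 point at 0.3 SD, 2 to 3 points at 0.5 SD and 4 to 6 points at 0.8 SD, whichever kind of list is used.

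**Step 5: balance, relevant only if the lists are unrestricted.** The exact binomial chance of a 60:40 or worse split within a stratum is 36% for 30 parents, 20% for 50, 5.7% for 100 and 1.8% for 150. The arms differ by 10 points or more in stratum share in 28% to 32% of trials at N=100 and in 12% to 15% at N=200. With blocks of 4 this never occurred. The mean absolute difference falls from 7.4–7.9 to 0.8–1.0 points at N=100. The cost of such imbalance is small: a 60:40 split loses 1 − 4 × 0.6 × 0.4 = 4% of that stratum's information.

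**The case against.** **The lists may be restricted.** A reader might infer from the spreadsheet generator and the number table that plain random numbers without blocks are used, so that stratification achieves nothing. The documents do not support that. A spreadsheet can produce permuted blocks, the plural (sequences) fits one list per stratum, and a stated 1:1 ratio is compatible with restriction. What stands is that no restriction is described.

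**Race/ethnicity is in some models anyway.** A reader might also infer that it enters only when the baseline test flags it. That is too broad, because the ANCOVA interactions and the moderator analyses use it regardless. What stands is narrower. The exploratory regressions for the main effect of condition do not fix it. For the ANCOVAs, the SAP does not say whether the main effect comes from the model with the interaction, or whether race/ethnicity is coded as the two-level stratum.

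**The two complaints need opposite designs.** Overstated standard errors arise only with restricted lists, and poor balance only with unrestricted ones. They cannot be added together. This stands. But the stratum is left unfixed either way, and the power loss is similar under both.

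**The consequences are limited.** Neither case inflates false positives. The objective is feasibility, the efficacy analyses are labelled exploratory, and pretest adjustment may already absorb part of any stratum effect. The descriptive feasibility criteria (mean scores above 3.0, completion of at least 70%) do not depend on balance between arms. All of this stands, and it sets the severity.

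**Conclusion.** The concern holds as a flaw in the stated covariate rule, of minor severity. The plan stratifies on race/ethnicity and then leaves that factor's place in the main-effect regressions to a test that a well-stratified trial will almost never fail. With restricted lists the result is conservative inference, visible mainly at a large stratum effect (type I error 3.3% to 3.6% at 0.8 SD, close to nominal at 0.3 SD). With unrestricted lists the result is lost precision only. Under either, the power cost runs from under 1 point to about 6 points, and the upper end needs a 0.8 SD race/ethnicity effect that nothing in the documents establishes. These figures rest on the assumed N, stratum share, effect sizes and 5% level.

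The absence of a described restriction is a secondary reporting gap. The documents do not show that stratification fails to balance the arms, nor that false-positive rates are raised.

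**What to change.** **Analysis (main change).** Pre-specify the two-level race/ethnicity stratum, as used at randomisation, as a fixed covariate in every between-arm ANCOVA and regression, whatever the baseline test shows. Say which model supplies the main effect of condition where interactions are also fitted.

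**Allocation (secondary).** State whether and how the sequences are restricted within strata. If allocation is not complete, use permuted blocks of randomly varied size (for example 4 and 6) separately in each stratum. If it is complete, report how the lists were made.

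**Cost.** One model term from data already collected in the eligibility screener, a sentence of reporting and, if still possible, a different list-generation step. No extra participants or data are needed, so this is a free improvement.
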